7.2. Study Endpoints

7.2.1. Primary Study Endpoints

The primary study endpoint will be left ventricular ejection fraction (LVEF) <50% diagnosed by echocardiography during pregnancy or within 12 months postpartum

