4.1. Inclusion Criteria

- Adult female age 18 – 49 years
- Currently pregnant or within 12 months postpartum
- Willing and able to provide informed consent

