4.2. Exclusion Criteria

- Under 18 years of age
- Complex congenital heart disease (single ventricle physiology or significant shunts with cardiac structural changes)
- Significant conduction abnormalities (ventricular pacing on recorded ECG, pacemaker dependence, or severely abnormal/bizarre QRS morphology on ECG tracings)
- Unable or unwilling to provide consent

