4.3.1 Screening, Recruitment, and Enrollment Plan

The local site investigator and/or study coordinator will pre-screen potential participants by reviewing medical records of patients already seen or newly identified patients. A study staff member will present the study information to the potential participants during a clinic or hospital encounter. If the participant is interested and willing to consent immediately, then an approved study staff will review the informed consent process with the participant. If the participant needs additional time to think about the study and participation, they will be given a copy of the informed consent form (ICF), and any other related IRB study approved document(s). Study staff will follow up with the potential participant at 1-2 weeks to learn if he/she is still interested and would like to participate. If a potential participant is still interested, a screening visit will be scheduled to review the ICF to obtain signatures required to enroll in the study.

The site Study Coordinator/staff will utilize the steps that follow to screen participants for the study. A detailed operational plan along with templates (i.e., screening logs) is contained in the Study Protocol Manual of Operations.

I. Pre-Screening Phase

- a. Potential participant will be identified during clinic or hospital encounters

II. Screening Phase

- a. Study staff will meet with potential participant to explain the study
- b. Study staff will confirm that participant meets eligibility criteria
- c. Study staff will have the participant sign an Informed Consent Form and provide copies to participant while placing originals in participant file.
- d. Study staff will collect contact information for participant

The study coordinators will be hired and trained locally to present the trial information without bias or pressure and in a culturally appropriate manner. Translators will be used at the local site as needed. Screening and enrollment failures and related reasons for same will be discussed at the monthly review meetings and potential actions will be taken as need. Attention will be paid to adhering to regulatory issues.

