6.1. Schedule of Events

6.1.1 - Control Arm

Assessment	Screening	Baseline, Randomization Visit 1	Visits 2 -7
------------	-----------	---------------------------------------	-------------

Inclusion/Exclusion Criteria	X	X	
Informed Consent ^a		X	
Demographics		X	
Clinical Assessments ^b		X	X
Medical History		X	
New Clinical Diagnosis			X
Current Medications		X	
Blood Chemistries ^c		X	
Hematology ^d		X	
Urine Analysis ^e		X	X
Inclusion/Exclusion Criteria	X	X	
Enrollment/Randomization		X	
12 lead ECG		X	X
AI-ECG – Sex and Age Determination		X	X

^aConsent may be obtained prior to baseline/randomization visit^bHeight, weight, blood pressure and heart rate^cTo be abstracted from medical records – Serum Cr, eGFR^dTo be abstracted from medical records – Hemoglobin (g/dl) or Hematocrit (%) or Packed Cell Volume; Hemoglobin Genotype (Hb AA, AS, SS, Sc); Rhesus factor (negative or positive), infectious screen.^eTo be abstracted from medical records – Positive for proteins (Yes or No)

6.1.2 - Intervention Arm

Assessment	Screening	Baseline, Randomization Visit 1	Visits 2-7
Inclusion/Exclusion Criteria	X	X	
Informed Consent ^a		X	
Demographics		X	
Clinical Assessments ^b		X	X
Medical History		X	
New Clinical Diagnosis			X
Current Medications		X	
Blood Chemistries ^c		X	
Hematology ^d		X	
Urine Analysis ^e		X	X
Enrollment/Randomization		X	
12 lead ECG		X	X
AI-ECG - Sex, Age, and Cardiomyopathy Determination		X	X
Portable ECG ^f		X	X
Echocardiogram ^g *		X	

^aConsent may be obtained prior to baseline/randomization visit^bHeight, weight, blood pressure and heart rate^cTo be abstracted from medical records – Serum Cr, eGFR^dTo be abstracted from medical records – Hemoglobin (g/dl) or Hematocrit (%) or Packed Cell Volume; Hemoglobin Genotype (Hb AA, AS, SS, Sc); Rhesus factor (negative or positive), infectious screen.^eTo be abstracted from medical records – Positive for proteins (Yes or No)^fPortable ECGs will be performed only among those in the intervention arm

^gEchocardiograms will be performed on all participants in the intervention arm at baseline and *if any new subsequent ECGs flag positive based on the AI-ECG predictions for cardiomyopathy (low ejection fraction) provided the baseline echocardiogram was normal. Participants with cardiomyopathy detected at any time point during the study will have a repeat echocardiogram at the end of study participation or 12 months postpartum (whichever is earlier) to assess for left ventricular recovery.

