7.2.2. Secondary Study Endpoints

Our secondary endpoints will include:

- A composite outcome of all-cause mortality and adverse cardiovascular events (including cardiomyopathy or systolic heart failure, diastolic heart failure, hypertensive disorders of pregnancy, preeclampsia/eclampsia, valvular heart disease, heart failure-related hospitalization, sustained ventricular arrhythmias, resuscitated cardiac arrest, and other pregnancy-related complications)
- Identification of LVEF $\leq 35\%$, $< 40\%$ and $< 45\%$ at any time among study participants during the study period
- Impact of AI-enabled ECG screening on echocardiography utilization

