7.3. Statistical Hypotheses and planned analyses

7.3.1. Descriptive Statistics

Descriptive statistics including measures of central tendency for numeric variables and frequency distributions for categorical variables will be calculated, as appropriate for all variables. Demographic, clinical, and outcome variables (primary and secondary) will be tabulated for all enrolled study participants. These data will be summarized for the entire cohort and stratified by randomized group and region. We will summarize the measures of diagnostic performance (i.e., AUC, sensitivity, specificity) stratified by study entry to account for the differential follow-up testing that may have occurred as a result of the AI-ECG screening

7.3.2. Primary Hypothesis:

AI-ECG is an effective tool to screen for cardiomyopathy, defined as LVEF < 50%, in pregnant women.

Statistical Hypothesis:

- $H_0: P_{\text{ai-ecg}} = P_{\text{control}}$
- $H_A: P_{\text{ai-ecg}} \neq P_{\text{control}}$

Where P defines the proportion of participants that have documented LVEF <50% by the conclusion of the study.

Primary analysis: A chi-square test without continuity correction will be applied to the resulting two by two table (rows: random treatment assignment, columns LVEF < 50% reported by conclusion of the study). The primary analysis will be conducted at the alpha=0.05 level of significance (two-sided).

7.3.3. Secondary Hypotheses:

AI-ECG will provide consistent performance across race, ethnicity, and postpartum enrollment status.

Secondary analysis: The introduction of stratification factors of race, ethnicity and postpartum status (all unique tables) will be used to produce a stratified contingency table. The Breslow-Day test of homogeneity of the odds ratio will be used to test for effect modification (differential treatment effects by strata). There is the potential for sparse strata with this analysis. If the odds ratio is not estimatable due to zero cells, the empirical logit estimator as well as pooled strata (to increase sample size for each strata) will be utilized.

An AI-ECG is an effective tool to screen for cardiomyopathy at different LVEF cut-off values (<45%, <40%, ≤ 35%).

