7.4.4. Analysis Sets

The analysis set for this study will follow the modified intention to treat principle. To be included in the analysis, the participant needs to be randomized and complete at least the baseline assessments and testing.

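### The primary event is not limited to LVEF <50% first documented after randomisation, so a woman with known low LVEF can count as a detection, and the protocol re-images her only in the intervention arm

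*Combined protocol and SAP*

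**What the plan says.** **Event.** Section 7.2.1 defines the primary endpoint as "left ventricular ejection fraction (LVEF) <50% diagnosed by echocardiography during pregnancy or within 12 months postpartum". The window is set by the pregnancy, not by randomisation. Section 7.3.2 defines the tested quantity: "Where P defines the proportion of participants that have documented LVEF <50% by the conclusion of the study". That gives an end and no start.

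**Lower cut-offs.** Section 7.2.2 counts LVEF ≤35%, <40% and <45% "at any time among study participants during the study period". The same measurement therefore has two windows within section 7.2, and neither excludes a case that was already known.

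**Who can enter.** Section 4.1 admits women "Currently pregnant or within 12 months postpartum", so part of the endpoint window can lie before randomisation. The cardiac exclusions in section 4.2 are "Complex congenital heart disease (single ventricle physiology or significant shunts with cardiac structural changes") and significant conduction abnormalities. Known low LVEF and previous cardiomyopathy are not listed. Under section 4.3.1 site staff "will pre-screen potential participants by reviewing medical records of patients already seen or newly identified patients".

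**Who is analysed.** Section 7.4.4: "To be included in the analysis, the participant needs to be randomized and complete at least the baseline assessments and testing". This removes no known case.

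**Who is imaged.** Under section 6.1.2, echocardiograms "will be performed on all participants in the intervention arm at baseline", whatever the history or AI-ECG result. The control schedule in 6.1.1 has no study echocardiogram.

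**The concern.** Secondary objective (a) in section 2.2 asks whether the AI-ECG improves detection. A woman whose low LVEF was on record before she was randomised has not been detected by the AI-ECG. Yet if her LVEF is still below 50% at the baseline study echocardiogram, she meets the endpoint.

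Randomisation balances how many such women each arm contains. It does not balance how often they are counted. In the intervention arm the protocol re-documents them. In the control arm a known case counts only if a clinical echocardiogram is done, or if one from before randomisation is accepted. Unequal counting inflates the estimated difference. Equal counting adds the same background rate to both arms and lowers power.

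**Working it through.** **1. The plan's own figure.** Section 7.1 gives 1% vs 4%, alpha 0.05, 80% power and 424 per group. The pooled-variance formula is n = [1.96√(2p̄(1−p̄)) + 0.842√(p₁(1−p₁)+p₂(1−p₂))]² / (p₂−p₁)². With p₁ = 0.01, p₂ = 0.04 and p̄ = 0.025 it gives 424. The plan's arithmetic is sound. All power and rejection figures below come from exact binomial enumeration of the test in section 7.3.2 (chi-square without continuity correction, two-sided 0.05). They are given at 500 per arm (section 7.1) and 600 per arm (the 1,200 accrual target at 1:1). Exact power at 1% vs 4% is 89% and 94%.

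**2. Inflation of the difference.** Let q be the share of women with known low LVEF or cardiomyopathy, r the share of these still below 50% at the baseline study echocardiogram, and c the share counted in the control arm.

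- Added to the intervention arm: q × r. Added to the control arm: q × c.
- Inflation: q × (r − c).

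The documents give none of the three. I assume q = 0.25% to 1%. The upper end equals the only Nigerian rate in the documents, 1 in 100 deliveries, but that is an incidence and not a share already known at entry. Setting r = 1 and c = 0 gives upper bounds:

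| q | Added, c = 0 | Share of the planned 3 points | Added, c = 0.5 |
|---|---|---|---|
| 0.25% | 0.25 points | 8% | 0.125 points |
| 0.5% | 0.5 points | 17% | 0.25 points |
| 1% | 1.0 point | 33% | 0.5 points |

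With r = 0.5 and c = 0 the additions halve: q = 1% adds 0.5 points.

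**3. Rejection when new-case rates are equal (1% in both arms, r = 1).** Control rate 1% + cq, intervention rate 1% + q. Baseline at q = 0: 4.3% at either size.

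| q | c = 0 (500 / 600) | c = 0.5 | c = 0.9 |
|---|---|---|---|
| 0.25% | 5.7% / 6.2% | 4.6% / 4.9% | 4.3% / 4.6% |
| 0.5% | 9.7% / 11.3% | 5.6% / 6.3% | 4.6% / 4.9% |
| 1% | 24.3% / 29.4% | 8.9% / 10.1% | 5.1% / 5.3% |

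**4. Rejection at the planned rates.** With q = 0.5% counted only in the intervention arm, 1% vs 4.5% gives 95% at 500 and 98% at 600, against 89% and 94%.

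**5. Equal counting in both arms, on top of 1% vs 4%.**

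| q | Rates | Power, 500 | Power, 600 |
|---|---|---|---|
| 0 | 1% vs 4% | 89% | 94% |
| 0.25% | 1.25% vs 4.25% | 85% | 91% |
| 0.5% | 1.5% vs 4.5% | 82% | 88% |
| 1% | 2% vs 5% | 75% | 82% |

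**6. What the fix does to power.** If 1% and 4% are new-case rates among women without known disease, coding known cases as non-events gives 1%(1−q) vs 4%(1−q). At q = 1% this is 0.99% vs 3.96%, with power 88.8% at 500 and 93.6% at 600, a loss of about 0.3 and 0.2 points. Section 7.1, however, takes the 1% from an incidence and supports the 4% with a pilot prevalence, so part of the 4% may be known disease:

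| New-case rates | n per arm for 80% | Power, 500 | Power, 600 |
|---|---|---|---|
| 1% vs 3.5% | 552 | 79% | 86% |
| 1% vs 3% | 769 | 64% | 72% |

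**The case against.** **The intended meaning is fairly clear.** Sections 3.1 and 6.2 describe record review as a way to see which outcomes develop. Section 6.1 separates baseline history from a new-diagnosis item at visits 2–7. Section 6.3 speaks of newly found cardiomyopathy. Section 7.1 expects no control diagnoses because there is no routine imaging, which makes sense only for diagnoses made in the study. This stands as evidence of intent, but none of that wording is tied to the endpoint or to the tested proportion. It does weaken one reading. Taken literally, 7.2.1 might count a woman whose low LVEF was recorded earlier in the same pregnancy and had recovered by baseline. The documents as a whole make that strained, and the point does not rest on it.

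**It restates the one-arm imaging problem.** In part: the intervention-only echocardiogram is the mechanism of unequal counting. But which cases may count is a separate question from how cases are found, and settling one does not settle the other.

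**The large rejection figures are extreme.** This stands. They need equal new-case rates although one arm is imaged throughout, little control capture, and no recovery. At q = 1% they also imply 2% total disease, twice the cited rate.

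**Known cases in the accuracy analysis.** A reader might infer that they contaminate the AUC analysis in 7.3.3. The documents do not support that: the reference is measured LVEF, and a woman whose LVEF is low now is a valid reference positive.

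**Material not seen.** The case report form is appended but not shown and may already hold a dated prior-status item. Section 7.4.5 promises a detailed analysis plan. The order of the list in 6.2.2 does not establish that history is taken after allocation.

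**Conclusion.** The concern holds as a gap in the event definition. Applied as written, sections 7.2.1 and 7.3.2 count a known, persisting case as an event, and sections 4.2 and 7.4.4 remove no such woman. The protocol guarantees her re-documentation only in the intervention arm.

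The size is uncertain because q, r and c are assumptions. At most (r = 1, c = 0), q = 0.25% to 1% adds 0.25 to 1.0 points to a planned difference of 3. Under equal 1% new-case rates, rejection at 600 per arm rises from 4% to between 6% and 29%, and is back to about 5% with 90% control capture. A reader might infer that the trial is likely to give a false-positive result for this reason. The documents do not support that: at the planned rates the decision changes little (94% to 98% at 600 per arm for q = 0.5%). The main harm is to the estimate and to its interpretation as detection. If known cases are counted equally instead, power at 600 per arm falls from 94% to 82–91%, still above the designed 80%; only q = 1% at 500 per arm (75%) falls below it.

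The point is secondary to the asymmetry from imaging one arm only. It should be corrected, but correcting it does not cure that asymmetry.

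**What to change.** - **Sections 7.2.1 and 7.3.2:** define the event as LVEF <50% first documented by an echocardiogram performed after randomisation, in a woman with no LVEF <50% or cardiomyopathy documented before randomisation. Use the same start in 7.2.2.
- **Denominator:** keep every woman in the section 7.4.4 analysis set, with known cases coded as non-events in both arms.
- **Prior status:** take it only from records or history dated before randomisation, captured identically in both arms, and never from the study baseline echocardiogram.
- **Sensitivity:** one analysis that counts any documented LVEF <50%, whether or not already known.
- **Section 7.1:** state whether the 1% and the 4% are new-diagnosis rates.

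**Cost.** Wording in three sections, one extra table and, unless the case report form already has it, a dated prior-status item. Staff already review medical records at pre-screening (section 4.3.1), so it can be recorded before allocation. The loss of power from coding known cases as non-events is about 0.3 points or less for q up to 1%, provided that 1% and 4% are new-case rates. The downside to state openly is that, if part of the 4% is known disease, the trial has less power for new cases than planned: 86% at 600 per arm and 79% at 500 for 1% vs 3.5%, and 72% and 64% for 1% vs 3%.

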7.2.2. Secondary Study Endpoints

Our secondary endpoints will include:

- A composite outcome of all-cause mortality and adverse cardiovascular events (including cardiomyopathy or systolic heart failure, diastolic heart failure, hypertensive disorders of pregnancy, preeclampsia/eclampsia, valvular heart disease, heart failure-related hospitalization, sustained ventricular arrhythmias, resuscitated cardiac arrest, and other pregnancy-related complications)
- Identification of LVEF $\leq 35\%$, $< 40\%$ and $< 45\%$ at any time among study participants during the study period
- Impact of AI-enabled ECG screening on echocardiography utilization

7.3. Statistical Hypotheses and planned analyses

7.3.1. Descriptive Statistics

Descriptive statistics including measures of central tendency for numeric variables and frequency distributions for categorical variables will be calculated, as appropriate for all variables. Demographic, clinical, and outcome variables (primary and secondary) will be tabulated for all enrolled study participants. These data will be summarized for the entire cohort and stratified by randomized group and region. We will summarize the measures of diagnostic performance (i.e., AUC, sensitivity, specificity) stratified by study entry to account for the differential follow-up testing that may have occurred as a result of the AI-ECG screening

7.3.2. Primary Hypothesis:

AI-ECG is an effective tool to screen for cardiomyopathy, defined as LVEF < 50%, in pregnant women.

Statistical Hypothesis:

- $H_0: P_{\text{ai-ecg}} = P_{\text{control}}$
- $H_A: P_{\text{ai-ecg}} \neq P_{\text{control}}$

Where P defines the proportion of participants that have documented LVEF <50% by the conclusion of the study.

Primary analysis: A chi-square test without continuity correction will be applied to the resulting two by two table (rows: random treatment assignment, columns LVEF < 50% reported by conclusion of the study). The primary analysis will be conducted at the alpha=0.05 level of significance (two-sided).

7.3.3. Secondary Hypotheses:

AI-ECG will provide consistent performance across race, ethnicity, and postpartum enrollment status.

Secondary analysis: The introduction of stratification factors of race, ethnicity and postpartum status (all unique tables) will be used to produce a stratified contingency table. The Breslow-Day test of homogeneity of the odds ratio will be used to test for effect modification (differential treatment effects by strata). There is the potential for sparse strata with this analysis. If the odds ratio is not estimatable due to zero cells, the empirical logit estimator as well as pooled strata (to increase sample size for each strata) will be utilized.

An AI-ECG is an effective tool to screen for cardiomyopathy at different LVEF cut-off values (<45%, <40%, ≤ 35%).

Secondary analysis: Within the intervention arm that obtains Echos as a part of the study protocol, the AI-ECG model performance will be evaluated. First, the existing algorithm, without retraining, will be used to evaluate discrimination (area under the receiver operating characteristics curve) at various thresholds for LVEF (i.e., 50% as planned for the primary along with 45%, 40% and 35% as noted here). Performance of the model by the patient stratification factors of Age, Race, Ethnicity, and postpartum status will be considered. For these, the reporting standards outlined in the STARD criteria will be adhered to, e.g., inclusion of measures of precision (confidence intervals) and fractional values associated with measures of performance.

7.3.4. Exploratory Hypotheses:

AI-ECG will improve the diagnosis of cardiovascular disease and associated clinical outcomes among pregnant and postpartum women.

Statistical plan: The analysis of this endpoint will use the same techniques as the primary and secondary analyses. Here, a composite score of any cardiovascular disease diagnoses during the course of the study will be utilized as the outcome measure.

An AI-enhanced point of care screening tool using portable, smartphone-compatible ECG devices (AIPOC-ECG) will be effective for the detection of cardiomyopathies among Black pregnant and postpartum women.

Statistical plan: The primary analysis will utilize the predictions based on the clinical 12 lead ECG machine. This exploratory analysis will compare the model performance on the point of care devices with the clinical standard ECG machine.

